8.2.2 Standardized photographs

In AD patients photographs will be taken of a representative area of AD involvement (the lesional area used for TEWL assessments) as well of a representative area without AD involvement (the non-lesional areas used for TEWL assessments) on day 1/baseline (pre dose). Subsequent photographs of the same area will be taken at each visit until Week 16 in AD patients.

In healthy volunteers photographs will be taken of a skin area corresponding to the lesional area of the AD patients, to which this healthy volunteer is matched on Day 1 at baseline. Subsequent photographs of the same area will be taken at each visit until Week 16 in HV.

For each image of each targeted lesional, non-lesional and healthy skin area morphologic parameters will be assessed by a validated method. The parameters may include size, color and other parameters. In addition each image will be scored by a blinded expert reader to grade the severity of skin findings.

Full body photographs will be taken for documentation purposes.

All photographs should be taken before the first TEWL assessment at each visit.

A separate photography ICF will be signed by study participants to confirm agreement to photography publication. Photographs are mandatory to be taken in all subjects, but agreement to their publication is only mandatory for AD patients. Healthy volunteers can decline consent for photography publication but still participate in the study.

Further instructions for taking the photographs and additional information on the parameters to be analyzed will be provided in the study reference manual.

8.2.3 Questionnaires and patient reported outcome assessments (PROs)

Questionnaires and patient-reported assessments will only be conducted in AD patients. Patient reported outcomes will be collected in an appropriate form, for which the respective device, diary and/or instruction is handed out to the patient at the screening (or baseline) visit. The electronic diary will be only used by the subset of patients who speak fluently the language in which adequate translations (ie, validated translations where applicable) are available. These Patient-Reported Outcome (PRO) questionnaires and NRS should be completed by the patients before the TEWL assessment at each visit and in a quiet place. The questionnaires should be completed by the patients themselves, independently from their physician, the study nurse or any other medical personnel and without any help from friends or relatives.

Patients will bring the diary to the site at each visit. Diary will be reviewed for any questionnaires omission and dispensed back to patients at each visit.

8.2.4 Investigator's Global Assessment (IGA)

The IGA is an assessment scale used in clinical studies to determine severity of AD and clinical response to treatment based on a 5-point scale ranging from 0 (clear) to 4 (severe). The IGA score will be assessed at time points according to [Section 1.3](#). IGA will be required for inclusion decision and is only be collected at screening.

The IGA will be provided in the study reference manual.

8.2.5 Individual Signs Score (ISS)

The ISS -also called Global Individual Signs Score (GISS)- is an assessment scale used to evaluate individual components of the AD lesions (erythema, edema/papulation, excoriations, and lichenification) by the investigator based on a 4-point scale ranging from 0 (none) to 3 (severe). The ISS score on erythema and edema/papulation will be assessed at time points according to [Section 1.3](#).

The ISS will be provided in the study reference manual.

8.2.6 Eczema Area and Severity Index (EASI)

The EASI is a validated measure used in clinical practice and clinical trials to assess the severity and extent of AD (26). The EASI is a composite index with scores ranging from 0 to 72. Four AD disease characteristics (erythema, thickness [induration, papulation, and edema], scratching [excoriation], and lichenification) will each be assessed for severity by the investigator or designee on a scale of “0” (absent) through “3” (severe). In addition, the area of AD involvement will be assessed as a percentage by body area of head, trunk, upper limbs, and lower limbs, and converted to a score of 0 to 6. In each body region, the area is expressed as 0, 1 (1% to 9%), 2 (10% to 29%), 3 (30% to 49%), 4 (50% to 69%), 5 (70% to 89%), or 6 (90% to 100%). The EASI will be collected at time points according to [Section 1.3](#).

The EASI assessment tool will be provided in the study reference manual.

8.2.7 Severity Scoring of Atopic Dermatitis (SCORAD)

The SCORAD is a validated tool used in clinical research and clinical practice that was developed to standardize the evaluation of the extent and severity of AD (27). The extent of AD is assessed as a percentage of each defined body area and reported as the sum of all areas, with a maximum score of 100% (assigned as “A” in the overall SCORAD calculation). The severity of 6 specific symptoms of AD is assessed using the following scale: none (0), mild (1), moderate (2), or severe (3) (for a maximum of 18 total points, assigned as “B” in the overall SCORAD calculation). Subjective assessment of itch and sleeplessness is recorded for each symptom by the patient or relative on a visual analogue scale (VAS), where 0 is no itch (or sleeplessness) and 10 is the worst imaginable itch (or sleeplessness), with a maximum possible score of 20. This parameter is assigned as “C” in the overall SCORAD calculation.

The SCORAD is calculated as: $A/5 + 7B/2 + C$. Patients will undergo this assessment at time points according to [Section 1.3](#).

The SCORAD assessment tool will be provided in the study reference manual.

8.2.8 Patient Oriented Eczema Measure (POEM)

The POEM is a 7-item, validated questionnaire used in clinical practice and clinical trials to assess frequency of disease symptoms in children and adults (28). The format is a response to 7 items (dryness, itching, flaking, cracking, sleep loss, bleeding, and weeping) based on frequency during the past week (ie, 0 = no days, 1 = 1 to 2 days, 2 = 3 to 4 days, 3 = 5 to 6 days, and 4 = all days) with a scoring system of 0 to 28; the total score reflects disease-related severity. The questionnaire will be administered at time points according to SoA ([Section 1.3](#)).

The POEM will be provided in the study reference manual.

8.2.9 Dermatology life quality index / Children's dermatology life quality index

The DLQI is a 10-item, validated questionnaire used in clinical practice and clinical trials to assess the impact of AD disease symptoms and treatment on Quality of Life (QOL) (29). The

format is a simple response to 10 items, which assess QOL over the past week, with an overall scoring system of 0 to 30; a high score is indicative of a poor QOL. The questionnaire is adapted to patient age and will be administered at time points according to [Section 1.3](#). CDLQI is the respective, validated version of DLQI to be used in adolescents (30).

The DLQI/CDQLI will be provided in the study reference manual.

8.2.10 Peak Pruritus Numerical Rating Scale (Peak Pruritus NRS)

The Peak Pruritus NRS is a simple assessment tool that patients will use to report the intensity of their pruritus (itch) during a daily recall period. Patients will be asked the following questions:

“On a scale of 0 to 10, with 0 being ‘no itch’ and 10 being the ‘worst itch imaginable’, how would you rate your itch at the worst moment during the previous 24 hours?”

Patients will complete the rating scale daily from Day-7 until Day 29, and then until Day 113 (EoT) at the week before the visits as indicated at [Section 1.3](#).

The Peak Pruritus NRS will be provided in the study reference manual.

8.2.11 Quality of Sleep NRS

Quality of Sleep NRS to collect information on patient-reported quality of sleep. Numerical rating scale range is from 0 (“worst possible sleep”) to 10 (“best possible sleep”).

Patients will complete the rating scale daily from Day-7 until Day 29, and then until Day 113 (EoT) at the week before the visits as indicated at [Section 1.3](#).

The Quality of Sleep NRS will be provided in the study reference manual.

8.3 SAFETY ASSESSMENTS

Planned time points for all safety assessments are provided in the SoA.

8.3.1 Physical examinations

- A complete physical examination will include, at a minimum, assessments of the skin, the cardiovascular, respiratory, and neurological systems. Height and weight will also be measured and recorded.
- Signs and symptoms of hypersensitivity reaction (if any) will be documented.
- A skin focused physical examination will be performed prior to TEWL assessments at time points according to [Section 1.3](#) and [Section 1.4](#).
- Investigators should pay special attention to clinical signs related to previous serious illnesses.
- Any new finding or worsening of previous finding should be reported as a new adverse event.

8.3.2 Vital signs

Vital signs, including heart rate, blood pressure, body temperature, and respiration rate, will be collected prior to TEWL assessments at time points according to [Section 1.3](#) and [Section 1.4](#). Heart rate, respiratory rate and blood pressure will be measured with the patient in sitting position, after the patient has rested comfortably for at least 5 minutes.

8.3.3 Laboratory testing

Urinalysis for pregnancy testing

Pregnancy testing will be performed for all women of childbearing potential. Urine pregnancy testing will be performed at time points according to [Section 1.3](#) and [Section 1.4](#).

8.3.4 Electrocardiograms

No ECG assessments will be required in this study.

8.3.5 Clinical safety laboratory assessments

No clinical safety laboratory assessments are required in this study.

8.3.6 Suicidal ideation and behavior risk monitoring

Not applicable for this study.

8.4 ADVERSE EVENTS AND SERIOUS ADVERSE EVENTS

AE will be reported by the participant (or, when appropriate, by a caregiver, surrogate, or the participant's legally authorized representative).

The Investigator and any qualified designees are responsible for detecting, documenting, and recording events that meet the definition of an AE or SAE and remain responsible for following up AEs that are serious, considered related to the study intervention or study procedures, or that caused the participant to discontinue the study intervention (see [Section 7](#)).

8.4.1 Time period and frequency for collecting Adverse Events (AE) and Serious Adverse Events (SAE) information

All SAEs will be collected from the signing of the informed consent form (ICF) until the follow-up visit at the time points specified in the SoA ([Section 1.3](#) and [Section 1.4](#)).

All AE will be collected from the signing of the ICF at the time points specified in the SoA ([Section 1.3](#) and [Section 1.4](#)).

All SAEs and adverse events of special interest (AESI) will be recorded and reported to the Sponsor or designee immediately and under no circumstance should this exceed 24 hours, as

indicated in Appendix 3 ([Section 10.3](#)). The Investigator will submit any updated SAE data to the Sponsor within 24 hours of it being available.

Investigators are not obligated to actively seek AE or SAE after conclusion of the study participation. However, if the Investigator learns of any SAE, including a death, at any time after a participant has been discharged from the study, and he/she considers the event to be reasonably related to the study intervention or study participation, the Investigator must promptly notify the Sponsor.

8.4.2 Method of detecting AEs and SAEs

The method of recording, evaluating, and assessing causality of AE and SAE and the procedures for completing and transmitting SAE reports are provided in Appendix 3 ([Section 10.3](#)).

Care will be taken not to introduce bias when detecting AEs and/or SAEs. Open-ended and non-leading verbal questioning of the participant is the preferred method to inquire about AE occurrences.

8.4.3 Follow-up of AEs and SAEs

After the initial AE/AESI/SAE report, the Investigator is required to proactively follow each participant at subsequent visits/contacts. At the pre-specified study end-date, all SAEs, AEs of special interest (as defined in [Section 8.4.8](#)), will be followed until resolution, stabilization, the event is otherwise explained, or the participant is lost to follow-up (as defined in [Section 7.3](#)). Further information on follow-up procedures is provided in Appendix 3 ([Section 10.3](#)).

8.4.4 Regulatory reporting requirements for SAEs

- Prompt notification within 24 hours by the Investigator to the Sponsor of a SAE is essential so that legal obligations and ethical responsibilities towards the safety of participants and the safety of a study intervention under clinical investigation are met.
- The Sponsor has a legal responsibility to notify both the local regulatory authority and other regulatory agencies about the safety of a study intervention under clinical investigation. The Sponsor will comply with country-specific regulatory requirements relating to safety reporting to the regulatory authority, Institutional Review Boards (IRB)/Independent Ethics Committees (IEC), and Investigators.
- Adverse events that are considered expected will be specified in the reference safety information.
- Suspected unexpected serious adverse reactions (SUSARs) are reported to regulatory authorities, Investigators, and IRBs/IECs as follows:
 - For SUSARs that are life-threatening or result in death, reporting is no later than 7 days after first knowledge by the Sponsor, with all relevant follow-up information subsequently reported within an additional 8 days

- For SUSARs, other than those that are life-threatening or result in death, reporting is no later than 15 days after first knowledge by the Sponsor
- An Investigator who receives an Investigator safety report describing a SAE, SUSAR or any other specific safety information (eg, summary or listing of SAEs) from the Sponsor will review and then file it along with the Investigator's Brochure and will notify the IRB/IEC, if appropriate according to local requirements. It is the responsibility of the Sponsor to assess whether an event meets the criteria for a SUSAR, and therefore, is expedited to regulatory authorities.

8.4.5 Pregnancy

- Details of all pregnancies in female participants will be collected after the start of study intervention and until 12 weeks after EoS.
- If a pregnancy is reported, the Investigator should inform the Sponsor within 24 hours of learning of the pregnancy and should follow the procedures outlined in Appendix 4 ([Section 10.4](#)).
- Abnormal pregnancy outcomes (eg, spontaneous abortion, fetal death, stillbirth, congenital anomalies, ectopic pregnancy) are considered SAEs.

8.4.6 Cardiovascular and death events

Not applicable.

8.4.7 Disease-related events and/or disease-related outcomes not qualifying as AEs or SAEs

Not applicable.

8.4.8 Adverse event of special interest

An AESI is an AE (serious or nonserious) of scientific and medical concern specific to the Sponsor's product or program, for which ongoing monitoring and immediate notification by the Investigator to the Sponsor is required. Such events may require further investigation in order to characterize and understand them. Adverse events of special interest may be added, modified or removed during a study by protocol amendment.

The following events are AESIs and require reporting to the Sponsor within 24 hours of learning of the event:

- Anaphylactic reactions.
- Systemic hypersensitivity reactions.
- Helminthic infections.
- Any severe type of conjunctivitis or blepharitis.

- Keratitis.
- Clinically symptomatic eosinophilia (or eosinophilia associated with clinical symptoms).

The following events also require reporting to the Sponsor within 24 hours of learning of the event:

- Pregnancy of a female subject entered in a study as well as pregnancy occurring in a female partner of a male subject entered in a study with IMP.
 - Pregnancy occurring in a female participant entered in the clinical trial or in a female partner of a male participant entered in the clinical trial. It will be qualified as an SAE only if it fulfills one of the seriousness criteria
 - In the event of pregnancy in a female participant, investigational medical product (IMP) should be discontinued.
 - Follow-up of the pregnancy in a female participant or in a female partner of a male participant is mandatory until the outcome has been determined
 - Abnormal pregnancy outcomes (eg, spontaneous abortion, fetal death, stillbirth, congenital anomalies, ectopic pregnancy) are considered SAEs
- Significant alanine transaminase (ALT) elevation
 - ALT >5 x the upper limit of normal (ULN) in participants with baseline ALT \leq 2 x ULN;or
 - ALT >8 x ULN if baseline ALT >2 x ULN
- Symptomatic overdose (serious or nonserious) with IMP
 - An overdose (accidental or intentional) with the IMP is an event suspected by the Investigator or spontaneously notified by the participant and defined as at least twice the intended dose during an interval of less than 11 days. The circumstances (ie, accidental or intentional) should be clearly specified in the verbatim and symptoms, if any, entered on separate adverse event forms.

The definitions of an AE or SAE can be found in the study protocol.

AE will be reported by the participant (or, when appropriate, by a caregiver, surrogate, or the participant's legally authorized representative).

The Investigator and any qualified designees are responsible for detecting, documenting, and recording events that meet the definition of an AE or SAE and remain responsible for following up AEs that are serious, considered related to the study procedures, or that caused the participant to discontinue the study (see study protocol).

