1.2 SCHEMA

Figure 1 - Graphical study design

LPS15991

AD Atopic dermatitis
 HV Healthy volunteers
 W Week
 BL Baseline
 EoT End of Treatment
 EoS End of Study

Dupilumab in AD patients: D1 (V02,W0) baseline
 D15±2days (V06, W2)
 D29±2days (V08, W4),
 D43±2days (V09, W6),
 D57±3days (V10, W8)
 D71±3days (W10 Dupilumab at home)
 D85±3days V11, W12)
 D99±3days (W14, Dupilumab at home)

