			D4 ±2 days	D8 ±2 days	D11 ±2 days	D15 ±2 days	D22 ±2 days	D29 ±2 days	D43 ±2 days	D57 ±3 days	D85 ±3 days				
Day	D-28 to D-1	D 1												UNSCH	
Week		W0	W1			W2	W3	W4	W6	W8	W12	W16	W20		
Visits	V01	V02	V03	V04	V05	V06	V07	V08	V09	V10	V11	V12	V13		
Quality of sleep NRS ^g		X	X	X	X	X	X	X	X	X	X	X		(X)	X
Safety															
Adverse event collection	X	X	X	X	X	X	X	X	X	X	X	X	X	X	X
Height		X													
Body weight		X										X			X
Vital signs ^d	X	X								X		X		(X)	X
Physical examination	X	X ^k										X ^k			X ^k
Pregnancy test (urine), WOCBP only ^e	X	X						X		X	X	X			
DNA sampling for filaggrin gene sequencing		X													
Optional assessments															
DNA sampling for future research		X													
Biomarker research samples (serum and plasma)		X										X			X

a EoS safety follow-up by phone.

b Loading dose dupilumab arm 600 mg (300 mg x 2 ie, two 300 mg syringes) for all adult patients and for those adolescents weighing 60 kg and above, and 400 mg (200 mg x 2 ie. two 200 mg syringes) for adolescent patients below 60 kg, followed by bi-weekly SC dosing of 300 mg dupilumab to adults and adolescents weighing 60 kg and above and bi-weekly SC dosing of 200 mg to adolescents weighing below 60 kg. Dupilumab administration on following days: D1 (V02,W0) baseline, D15±2days (V06, W2), D29±2days (V08, W4), D43±2days (V09, W6), D57±3days (V10, W8), D71±3days (W10; self-administration of dupilumab at home), D85±3days V11, W12), D99±3days (W14; self-administration of dupilumab at home).

c Assessments on treatment days are to be conducted before administration of dupilumab.

d Vital signs, including systolic and diastolic blood pressure (mmHg), pulse rate (beats per minute), body temperature (°C), and respiratory rate will be measured at Screening, Baseline at Week 0, Week 8, and Week 16 (EoT). Height (cm) will be measured at Baseline only. Body weight (kg) will be measured at Baseline, and Week 16 (EoT).

e Only for women of childbearing potential. Pregnancy will lead to definitive treatment discontinuation in all cases.

f DLQI will be used for adults; CDLQI will be used for adolescents.

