6.1 STUDY INTERVENTION(S) ADMINISTERED

Study participants will be assigned to study intervention as described below:

- Up to 24 adolescent and adult moderate to severe AD patients will receive dupilumab.
- For AD patients aged ≥ 12 to < 18 years the dose regimen will follow the table below and based on the body weight on Day 1 (the dose will not be changed during the study):

Body Weight	Loading Dose on Day 1	Subsequent Doses (Q2W)
less than 60 kg	400 mg (two 200 mg injections)	200 mg
60 kg or more	600 mg (two 300 mg injections)	300 mg

- AD patients age 18 years and older will receive a SC loading dose of 600 mg on Day 1, followed by 300 mg Q2W SC through Week 14. Drug will be administered by study site staff at baseline, Weeks 2, 4, 6, 8, 12. Drug will be self-administered by AD patients at Week 10 and 14.

One kit number list by dosage strength is generated centrally by Sanofi and IMP are packaged in accordance with these lists. The treatment will be given to the patient depending on their age and body weight.

Study intervention will be dispensed at the study visits summarized in SoA (see [Section 1.3](#)). Returned study intervention should not be re-dispensed to the participants.

Table 2 - Overview of study interventions administered

ARM name	Dupilumab 200	Dupilumab 300
Intervention name	Dupilumab 200 mg	Dupilumab 300 mg
Type	Biological/Vaccine	Biological/Vaccine
Dose formulation	A 175 mg/mL dupilumab solution in a pre-filled syringe to deliver 200 mg in 1.14 mL	A 150 mg/mL dupilumab solution in a pre-filled syringe to deliver 300 mg in 2 mL
Unit dose strength(s)	200 mg	300 mg
Dosage level(s)	200 mg every 14 \pm 2 or 3 days after an initial loading dose of 400 mg	300 mg every 14 \pm 2 or 3 days after an initial loading dose of 600 mg
Route of administration	Subcutaneous ^a	Subcutaneous ^a
Use	Experimental	Experimental
IMP	IMP	IMP

ARM name	Dupilumab 200	Dupilumab 300
Packaging and labeling	One glass pre-filled syringe packed in a patient kit box. Both the glass pre-filled syringe and the box will be labeled as required per country requirement.	One glass pre-filled syringe packed in a patient kit box. Both the glass pre-filled syringe and the box will be labeled as required per country requirement.
[Current/Former name(s) or alias(es)]	Dupixent®	Dupixent®

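### Dosing windows set around study days allow in-window doses 8 to 10 days apart, which conflicts with either the Table 2 interval or the overdose definition, depending on how Table 2 is read

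*Protocol*

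**What the plan says.** Three places in the protocol bear on the spacing of doses.

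- **Visit and dosing windows.** Footnote b to the AD patients' schedule (Section 1.3) fixes each dose to a study day. It starts with "Dupilumab administration on following days: D1 (V02,W0) baseline", which has no window, and continues "D15±2days (V06, W2), D29±2days (V08, W4), D43±2days (V09, W6), D57±3days (V10, W8", then "D71±3days (W10; self-administration of dupilumab at home", then "D85±3days V11, W12), D99±3days (W14; self-administration of dupilumab at home". Figure 1 (Section 1.2) repeats the set, for example "D71±3days (W10 Dupilumab at home".
- **Interval.** Table 2 (Section 6.1) sets the maintenance dose at every 14 days with a tolerance of 2 "or 3 days after an initial loading dose of 600 mg". The 200 mg column has the same tolerance after its own loading dose.
- **Overdose.** Section 8.4.8 describes an overdose as an event that the investigator suspects or the participant reports unprompted, "defined as at least twice the intended dose during an interval of less than 11 days". Symptomatic overdose is on the 24-hour reporting list. Section 8.5 covers any overdose, symptomatic or not: the Medical Monitor is contacted at once and the participant is monitored for at least 28 days.

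Neither footnote b nor Figure 1 adds a minimum gap between doses. Section 8.4.8 does not exempt doses given inside their windows.

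**The concern.** The windows are anchored to study days, not to the previous dose. When one dose is late and the next is early, the two tolerances add up, and the actual gap can be well short of 14 days although neither dose is off schedule. Two planned doses in such a gap are, on a plain count, double the intended amount in under 11 days.

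The stake is how on-schedule dosing is classified. One investigator could regard a pair of doses as fully compliant with the schedule. Another could regard the same pair as an overdose and start the Section 8.5 actions, with expedited reporting if there are symptoms. A safety rule should not depend on which page the site happens to consult.

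**Working it through.** **Inputs.** Nominal dosing days 1, 15, 29, 43, 57, 71, 85 and 99, with windows 0, ±2, ±2, ±2, ±3, ±3, ±3 and ±3 days (Section 1.3 footnote b; Figure 1). Table 2: 14 days ± 2 or 3. Section 8.4.8: limit of less than 11 days.

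**Reproducing the plan's own figures.** The nominal spacing is 14 days for all seven consecutive pairs, as stated. As an interval, Table 2 allows 14 − 2 = 12 to 14 + 2 = 16 days, or 14 − 3 = 11 to 14 + 3 = 17 days. Only the first pair reproduces this, because Day 1 has no window.

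**Formulas.**
- Shortest gap = (later day − its window) − (earlier day + its window).
- Longest gap = (later day + its window) − (earlier day − its window).
- With offsets *a* (earlier dose) and *b* (later dose) from nominal, gap = 14 + *b* − *a*. It is under 11 when *a* − *b* ≥ 4. If both dosing days are counted, the span is gap + 1, which is under 11 when *a* − *b* ≥ 5.

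| Pair | Shortest gap | Longest gap | In-window day pairs with gap under 11 | Same, both dosing days counted |
|---|---|---|---|---|
| D1–D15 | 13 − 1 = 12 | 17 − 1 = 16 | 0 of 5 | 0 of 5 |
| D15–D29 | 27 − 17 = 10 | 31 − 13 = 18 | 1 of 25 | 0 of 25 |
| D29–D43 | 41 − 31 = 10 | 45 − 27 = 18 | 1 of 25 | 0 of 25 |
| D43–D57 | 54 − 45 = 9 | 60 − 41 = 19 | 3 of 35 | 1 of 35 |
| D57–D71 | 68 − 60 = 8 | 74 − 54 = 20 | 6 of 49 | 3 of 49 |
| D71–D85 | 82 − 74 = 8 | 88 − 68 = 20 | 6 of 49 | 3 of 49 |
| D85–D99 | 96 − 88 = 8 | 102 − 82 = 20 | 6 of 49 | 3 of 49 |

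The last two columns count combinations of days. They are not probabilities, because the documents say nothing about when within a window patients are dosed.

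**Reading the table.** By date difference, six of seven gaps can fall below 11 days. Counting both dosing days, a 10-day gap spans 11 days and drops out, which leaves the four gaps from Day 43 onward. Each of the three 8-day gaps involves a home dose (Week 10 or Week 14). The longest gaps of 18 to 20 days also exceed Table 2's 17.

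**Limit within one patient.** Two adjacent gaps cannot both be under 11 days. Both would have to be 10 or less, so 20 days or less together, but the smallest two-gap total is 82 − 60 = 22 days (Day 57 to Day 85; the same for Day 71 to Day 99). At most three of the six gaps can therefore be short in any one patient.

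**Two readings of Table 2.**
- As a dose-to-dose interval, its minimum of 11 days fits the overdose limit exactly, but the schedule permits gaps of 8 to 10 and of 18 to 20 days. Footnote b and Figure 1 contradict Table 2.
- As shorthand for the visit windows (±2 early, ±3 later), Table 2 agrees with the schedule. In-window doses can then meet the numeric part of Section 8.4.8.

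**The case against.** The strongest reply is that a Table 2 breach and a permitted overdose cannot both be claimed at once. If Table 2 governs the interval, gaps under 11 days are not permitted, and Table 2 and Section 8.4.8 fit together. If Table 2 abbreviates the visit windows, nothing in it is breached. This is right, and the point is put here as one conflict or the other. Each reading still leaves a conflict. Under the first, a site working from the schedule is not told that Table 2 narrows its windows.

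Second, the overdose definition is more than a number. It needs investigator suspicion or a report from the participant, and the intended dose over an interval could be taken to mean whatever the schedule intends in that interval. This stands as a limit: a short gap meets the numeric part only and is not automatically an overdose. But the text does not say that scheduled doses are excluded.

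Third, short gaps need a late dose followed by an early one, and few day combinations produce them. This also stands. It bears on how often the problem would arise, not on whether the passages agree.

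A reader might go on to infer that short gaps would inflate the above-planned dosing counts or remove patients from the mITT population. The documents do not support either. Section 9.4.5.2 judges each administration against the planned dose and gives no interval criterion for above-planned dosing. SAP Section 1.2 excludes participants for major deviations that affect the assessment of efficacy data, and nothing suggests that a dose inside its window would be classed that way.

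**Conclusion.** The passages conflict as written. With every dose in its window, consecutive doses can be as little as 8 days apart. Six of seven gaps can be under 11 days by date difference, and four of seven if both dosing days are counted. The result is either a schedule that contradicts Table 2, or on-schedule doses that meet the numeric part of the overdose definition.

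The conclusion assumes that windows may be used freely at both ends, which the schedule does not forbid, and that two planned doses count as double the intended amount. The practical consequence is confined to safety handling: possible Medical Monitor contact and at least 28 days of monitoring under Section 8.5, and 24-hour reporting only if there are symptoms. It should not be read as saying that every short gap is a reportable overdose, and no effect on the primary endpoint or the analysis populations is shown. How often such gaps would occur cannot be judged from the documents.

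**What to change.** The sponsor should reconcile three items: the windows in Section 1.3 footnote b and Figure 1, the interval in Table 2, and the overdose interval in Section 8.4.8. After that, a dose permitted by the schedule should not also meet the overdose definition. The text should also state whether Table 2 describes the gap between doses or the visit window, and whether the overdose interval is a date difference or counts both dosing days. Which of the figures is right is for the sponsor to decide.

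In the analysis, add a listing of every dosing interval under 11 days, with its classification (within schedule, deviation or overdose) and whether symptoms were reported.

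The cost is a protocol clarification or non-substantial amendment plus one listing, built from the dosing information that Section 6.4 already requires in the eCRF.
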